## 9.4.2 Main Analyses of Secondary Efficacy Endpoints

Frequencies and percentages will be provided along with 95% CIs based on ITT 1 and ITT 2 populations using the AO approach. The attributes of the estimands corresponding to the secondary efficacy objectives are summarized in Table 4.

[figure not shown]

Table 4. Summary of the Estimand Attributes Corresponding to the Secondary Efficacy Objectives

		A	attributes of the	e Estimand	
Estimand Label	Treatment	Endpoint	Population	Handling of Intercurrent Events	Statistical Summary
Categorical secondary endpoints	Upadacitinib 15 mg or 30 mg	Achievement of each respective categorical endpoint	Subjects with moderate severe atopic dermatitis	The treatment policy strategy is used in this study. All the values for the variable of interest will be used regardless of Intercurrent Events.	Counts and percentages will be provided along with 95% CIs

# 9.4.3 Sensitivity and Supplementary Analyses for Secondary Efficacy Endpoints

There is no sensitivity or supplementary analysis for secondary efficacy endpoints.

[figure not shown]
# 9.5 Additional Efficacy Endpoints and Analyses

The additional efficacy endpoints listed in Section 3.3 will be analyzed as below. The categorical endpoints will be summarized by ITT 1 and ITT 2 populations using the AO approach. For the categorical endpoints, counts and percentages will be provided along with 95% CIs, by visit and by treatment group. For the continuous endpoints, Least Square (LS) mean, 95% CI and standard error (SE) will be provided using ANCOVA including treatment, baseline, stratification factors (vIGA-AD categories [3; 4] and prior use of dupilumab [yes; no]) in the model.

# 9.6 Efficacy Subgroup Analyses

The primary endpoint will be also summarized by the following subgroups using the AO approach:

- Baseline vIGA-AD (3; 4),
- Baseline EASI score ( $\langle 21; \geq 21 \rangle$ ), and
- Baseline EASI score (<median; ≥median).

• Prior Use of Dupilumab (Yes; No)

### 9.7 Analysis of Daily Efficacy Measurement

For daily efficacy assessments of the Worst Pruritus NRS, ADerm-IS sleep domain, and ADerm-SS skin pain, a rolling weekly average is calculated by using handheld device only to represent the corresponding endpoints by week in DB Period and SB Period.

The weekly average of the daily values from a maximum of 7 days immediately prior to the first dose date will be used as the Baseline value. The rolling weekly average score is calculated for each Day m, starting from Day 8 through the Week 24 visit as follows. Let  $P_{m-6}$ ,  $P_{m-5}$ , ...,  $P_{m-1}$ ,  $P_m$  be the daily score from Day m-6 to Day m, and  $N_m$  be the number of days with non-missing scores from Day m-6 to Day m, then the rolling weekly average for Day m is:

[figure not shown]
$$\frac{\sum_{i=m}^{m} P_i}{N_m}$$

If the values from four or more days of the 7-day period are missing, then the rolling weekly average of Day m will be set to missing. If more than one assessment is included on the same day, the assessment associated with the worst condition on that day will be chosen as the daily score. Analysis value for a given visit will be selected from rolling averages based on analysis window conventions.

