- Achievement of ADerm-IS Emotional State ≤ 2 / = 0 for subjects with ADerm-IS Emotional State
 > 2/> 0 at Baseline, respectively.
- Achievement of an improvement (reduction) in Atopic Dermatitis Symptom Scale (ADerm-SS)
 Skin Pain ≥ 4 from Baseline for subjects with ADerm-SS Skin Pain ≥ 4 at Baseline.
- Achievement of ADerm-SS Skin Pain ≤ 1 / = 0 for subjects with ADerm-SS Skin Pain > 1/> 0 at Baseline, respectively.
- Achievement of an improvement (reduction) in ADerm-SS 7-item total symptom score (TSS-7) ≥ 28 from Baseline for subjects with ADerm-SS TSS-7 ≥ 28 at Baseline.
- Achievement of ADerm-SS TSS-7 \leq 11 / \leq 1 for subjects with ADerm-SS TSS-7 > 11 / > 1 at Baseline, respectively.
- Achievement of EASI 75 / 90, for subjects who experienced an inadequate response to previous treatment with dupilumab for AD as reported by the investigator
- Achievement of EASI 90 and a Worst Pruritus NRS of 0 or 1, for subjects with Worst Pruritus NRS
 1 at Baseline and experienced an inadequate response to previous treatment with dupilumab for AD as reported by the investigator.
- Achievement of EASI 75 / 90, for subjects who were previously treated with dupilumab for AD.
- Achievement of EASI 90 and a Worst Pruritus NRS of 0 or 1, for subjects with Worst Pruritus NRS
 > 1 at Baseline and were previously treated with dupilumab for AD.
- For subjects participating in the Wearable Tool Substudy:
 - Change from Baseline in average nightly nocturnal scratch: total scratch time and number of scratch events.
 - Change from Baseline in the following sleep parameters: total sleep time, wake after sleep onset, sleep efficiency, and sleep onset latency.

For PROs that are assessed daily (Worst Pruritus NRS, ADerm-SS, ADerm-IS), the associated endpoints will also be analyzed daily for the initial 28 days of the double-blind treatment period and the initial 28 days of the single-blind treatment period.

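### SAP 9.7 lets the 7-day rolling average run across the Week 12 dose switch, so in SC1 and SC4 the averages on single-blind days 1 to 6 mix two doses

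*SAP*

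**What the plan says.** SAP 9.7 covers three scores: "For daily efficacy assessments of the Worst Pruritus NRS, ADerm-IS sleep domain, and ADerm-SS skin pain". For these it defines a rolling average: "The rolling weekly average score is calculated for each Day m, starting from Day 8 through the Week 24 visit as follows". The terms averaged are stated to "be the daily score from Day m-6 to Day m", so each value looks back over seven days. A value is set to missing only under this condition: "If the values from four or more days of the 7-day period are missing". Four scores are therefore enough, wherever in the window they lie.

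The section gives the averages a purpose, "to represent the corresponding endpoints by week in DB Period and SB Period", and says how a visit value is obtained: "Analysis value for a given visit will be selected from rolling averages based on analysis window conventions". Neither document sets out those conventions.

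At the start of treatment the plan keeps the periods apart. Baseline is the average "from a maximum of 7 days immediately prior to the first dose date will be used as the Baseline value", and the first on-treatment average, on Day 8, covers Days 2 to 8. No matching rule exists for the start of the single-blind period. At that point SC1 goes from 15 mg to 30 mg and SC4 from 30 mg to 15 mg, while SC2 and SC3 keep their dose (SAP 2.2).

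Protocol 3.4 also plans day-by-day analysis of the daily patient-reported endpoints for the first 28 days of each period, including "the initial 28 days of the single-blind treatment period". The SAP does not repeat this or say which form of the score it uses. SAP 14.1 declares no change from the protocol's planned analyses, so the analysis still stands.

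**The concern.** A window that always looks back six days will, just after a dose change, average scores from both doses. SC1 and SC4 are the cohorts named in the two primary objectives, and the days just after the switch are where an early itch response to escalation, or an early loss after reduction, would show. Averages that still contain old-dose days would understate such a change.

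The same series supplies the Week 12 itch value. Three kinds of Week 12 secondary endpoint use it (SAP 3.2): improvement of at least 4 points, a score of 0 or 1, and the composite of EASI 90 with a score of 0 or 1. These should describe the randomised dose only. If post-switch days entered, 30 mg days of escalated subjects would count in the 15 mg group, and 15 mg days of reduced subjects in the 30 mg group.

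**Working it through.** The point concerns a derivation rule, so there is no stated figure to reproduce.

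**Inputs**
- Window: Day m-6 to Day m; minimum four scores (SAP 9.7).
- Nominal days: Week 12 = Day 85, Week 16 = Day 113, Week 24 = Day 169 (Protocol Appendix D). The visit window is read as ±3 days; that row is damaged in the available text.
- Switching shares: 54% of SS1 and 65% of SS2; dropout at most 8% per 12 weeks; 454 subjects randomised 1:1 (SAP 2.2 and 2.4).
- Assumption: a score counts as new dose from the calendar day of the first single-blind dose.

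**1. Averages after the switch.** On single-blind day k (k = 1 to 7) the window holds k new-dose days and 7 - k old-dose days.

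| Single-blind day | Old-dose days of 7 | Share old dose |
|---|---|---|
| 1 | 6 | 86% |
| 2 | 5 | 71% |
| 3 | 4 | 57% |
| 4 | 3 | 43% |
| 5 | 2 | 29% |
| 6 | 1 | 14% |
| 7 | 0 | 0% |

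Six values per switching subject are mixed. With a first single-blind dose on Day 85 these are Days 85 to 90, and Day 91 is the first clean value.

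**2. Effect of the four-score minimum.** A value can rest wholly on old-dose scores when 7 - k ≥ 4, that is, on single-blind days 1 to 3.

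**3. Week 12 value, if taken on nominal Day 85.** The window is Days 79 to 85.

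| First single-blind dose | New-dose days of 7 |
|---|---|
| Day 82 | 4 (57%) |
| Day 85 | 1 (14%) |
| Day 86 or later | 0 |

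If the switch day is instead counted as old dose, the first two rows become 3 of 7 (43%) and 0 of 7, and the six mixed values move to single-blind days 2 to 7.

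**4. Later visits.** For a first single-blind dose on any of Days 82, 85, 86 or 88, averages ending on Days 110 and 113 (Week 16) and on Days 166 and 169 (Week 24) contain no old-dose days.

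**5. Subjects concerned.** Entering the single-blind period: 227 × 0.92 = 208.8 per sub-study, 417.7 in all. SC1: 208.8 × 0.54 = 112.8. SC4: 208.8 × 0.65 = 135.7. Together 248.5 of 417.7, or 59.5%.

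**The case against.** The strongest reply is that the mixed values may never be reported. Protocol 3.4 speaks of analysing the endpoints daily, whereas SAP 9.7 uses the rolling average to represent endpoints by week and then by visit. Rolling values begin on Day 8, so they cannot supply Days 1 to 7 of the double-blind daily analysis. That suggests plain daily scores for the 28-day analyses. The reply stands as an inference. Neither document says so, and 9.7, the SAP's section on daily measurements, describes only the rolling average.

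For Week 12, the reply is that the visit value probably belongs to the double-blind period. The SAP frames efficacy by period and cuts double-blind exposure (6.0) and adverse events (10.2.1) at the single-blind start. New drug is assigned and dispensed at the Week 12 visit, so with a Day 85 switch a Day 85 value contains at most one new-dose day. This also stands, but 9.7 contains no such cut and the windows are not given.

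A reader might go further and infer that the early itch curves after the switch are certainly diluted, or that the Week 12 itch results are contaminated. The documents support neither: the first needs rolling averages in the 28-day analysis, the second a visit value ending on or after the switch. Nor can an old-dose share of 86% be read as 86% shrinkage of a treatment effect. That would require an immediate, full step change on the first new-dose day, which no passage claims.

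**Conclusion.** The gap is real and follows from the stated formula: one unbroken series with no bound at the first single-blind dose. The certain effect is six mixed-dose averages per subject in SC1 and SC4. In SC2 and SC3 the window crosses periods but not doses. The rule covers Worst Pruritus NRS and two ADerm scores only; 9.7 gives no averaging rule for TSS-7, daily activities or emotional state.

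Whether any reported result changes depends on the two open points: the form of score used in the 28-day single-blind analysis, and the Week 12 window. The primary endpoint, other endpoints based on EASI alone, and all Week 16 and Week 24 values are untouched. The study is descriptive, so no test is at risk. The point is modest in weight but worth settling before database lock, because it concerns the cohorts of both primary objectives and costs very little to close.

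**What to change.** In SAP 9.7:

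1. State that no averaging window crosses the first single-blind dose date. Single-blind averages use only days on or after that date, and the Week 12 value uses only days before it. Using days strictly before the switch keeps the Week 12 value clean however the switch day is counted.
2. State that the 28-day daily analyses in Protocol 3.4 use the plain daily scores.

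The visit windows that 9.7 relies on should also be written out, or the document holding them named.

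The cost is two sentences and a date condition in the program. Mixed values fall from six per switching subject to none. The price is that the first few single-blind days have no rolling average: with the four-score minimum kept, the earliest value falls on single-blind day 4, and the first full seven-day average on day 7. Plain daily scores cover the gap.

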# 10.0 Safety Analyses

#### 10.1 General Considerations

Safety summaries will be provided using the safety Populations. For the safety analysis, subjects are assigned to a treatment group based on the treatment actually received, regardless of the treatment randomized.

Safety analyses will include adverse events, laboratory, and vital sign measurements. Missing safety data will not be imputed.

#### 10.2 Adverse Events

The summaries of adverse events will be provided by treatment groups in DB Period for Safety 1 Population, in SB Period for Safety 2 Population, and during the administration of upadacitinib for All UPA Population.

# 10.2.1 Treatment-Emergent Adverse Events

Treatment-emergent adverse events (TEAEs) are defined as follows:

- TEAEs in DB Period are defined as any adverse events that begin or worsen in severity after initiation of upadacitinib through the minimum (30 days following the last dose of upadacitinib in DB Period, or the start day of SB Period 1).
- TEAEs in SB Period are defined as any adverse events that begin or worsen in severity after initiation of upadacitinib in SB Period through 30 days following the last dose of upadacitinib in SB Period.
- TEAEs during the administration of upadacitinib are defined as any adverse events that begin or worsen in severity after initiation of upadacitinib through 30 days following the last dose of upadacitinib.

If a missing or an incomplete onset date is collected for an adverse event, the event will be assumed to be treatment-emergent unless there is other evidence that confirms that the event is not treatment-emergent (e.g., the event end date is prior to the study drug start date). Events where the onset date is the same as the study treatment start date are assumed to be treatment-emergent.

All TEAEs will be summarized overall, as well as by primary MedDRA SOC and Preferred Term. The SOCs will be presented in alphabetical order, and the PTs will be presented in alphabetical order within each SOC.

The number and percentage of subjects experiencing TEAEs and the number of events per 100 patient-years of exposure will be summarized.

TEAEs per 100 patient-years of exposure are defined as the number of TEAEs divided by the total exposure in 100 patient-years. See the calculation method below:

100 \* (Number of TEAEs) / (Total Patient Years)

where total patient years is defined as the sum of the study drug duration (defined in Section 6.0) of all subjects normalized by 365.25 and rounded to 1 decimal place.

#### 10.2.2 Adverse Event Overview

The number and percentage of subjects experiencing TEAEs will be summarized for each treatment group for the following AE categories:

- Any TEAE
- Any treatment-emergent serious adverse events (SAE)
- Any TEAE leading to discontinuation of study drug
- Any severe TEAE (Grade 3 and above according to National Cancer Institute (NCI) Common Terminology Criteria for Adverse Events (CTCAE), version 5.0)
- Any TEAE with reasonable possibility of being drug related
- Any treatment-emergent SAE with reasonable possibility of being drug related
- Any TEAE leading to death
- All Deaths
  - $\circ$  Deaths occurring  $\leq 30$  days after last dose of upadacitinib
  - Deaths occurring > 30 days after last dose of upadacitinib
  - o Related to COVID 19

In addition, a separate overview of AESIs and overview of AESIs per 100 patient-years of exposure will be provided for the categories in Section 10.2.6.

[figure not shown]
# 10.2.3 Treatment-Emergent Adverse Events by SOC and/or PT

TEAEs will be summarized and presented using primary MedDRA version 26.0 by system organ class (SOC) and preferred terms (PT); by maximum relationship to study drug as assessed by the investigator (e.g., reasonable possibility or no reasonable possibility) and SOC and PT; by maximum toxicity and SOC and PT. The SOCs will be presented in alphabetical order, and the PTs will be presented in alphabetical order within each SOC. Subjects reporting more than one adverse event for a given MedDRA preferred term will be counted only once for that term (most severe incident for the toxicity tables and most related incident for the relationship tables). A subject who reports more than 1 AE in different SOCs will be counted only once in the overall total. Subjects reporting more than one type of adverse event will be counted only once in the overall total. If the same adverse event occurs multiple times within a subject, the highest severity and level of relationship to investigational product will be reported.

The following summaries of adverse events will be generated:

- All TEAEs
- Treatment-emergent serious adverse events
- Treatment-emergent severe adverse events
- TEAEs with reasonable possibility of being drug related
- TEAEs leading to discontinuation of study drug
- TEAEs by maximum toxicity
- TEAEs of Special Interest
- TEAEs leading to death

For summaries of AEs by toxicity, each subject is counted only once—according to the maximum toxicity level observed. If a subject has an AE with an unknown toxicity, then the subject will be counted in the toxicity category of "unknown." The only exception is that if the subject has another occurrence of the same AE with the most extreme, non-fatal NCI CTCAE toxicity (i.e., grade 4) or is fatal (grade 5). In this case, the subject will be counted under grade 4 if non-fatal or 5 if fatal. For tables that look at severity instead of

toxicity, the subjects that have an unknown NCI CTCAE grade but another occurrence of the same AE that is considered severe (grade  $\geq$  3) will be counted under severe.

# 10.2.4 Treatment-Emergent Adverse Events per Patient-Years of Exposure

[figure not shown]
AEs occurring during the entire study will be presented by event rate per 100 patient years. These will be presented by treatment group for the following AE categories.

- Any TEAE
- Any treatment-emergent SAE
- Any TEAE leading to discontinuation of study drug
- Any severe TEAE
- Any TEAE with reasonable possibility of being drug related
- Any treatment-emergent SAE with reasonable possibility of being drug related
- TEAEs of Special Interest
- Any TEAE leading to death
- All Deaths
  - $\circ$  Deaths occurring  $\leq 30$  days after last dose of upadacitinib
  - Deaths occurring > 30 days after last dose of upadacitinib
  - Related to COVID 19

Additional AEs may be considered for tabulation/summary based on recommendations from Clinical and Safety as deemed appropriate.

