Important Medical Event Requiring Medical or Surgical Intervention to Prevent Serious Outcome An important medical event that may not be immediately life-threatening or result in death or hospitalization but based on medical judgment may jeopardize the subject and may require medical or surgical intervention to prevent any of the outcomes listed above (i.e., death of subject, life threatening, hospitalization, prolongation of hospitalization, congenital anomaly, or persistent or significant disability/incapacity). Additionally, any elective or spontaneous abortion or stillbirth is considered an important medical event. Examples of such events include allergic bronchospasm requiring intensive treatment in an emergency room or at home, blood dyscrasias or convulsions that do not result in inpatient hospitalization, or the development of drug dependency or drug abuse.

All adverse events reported from the time of study drug administration until 30 days after discontinuation of study drug administration will be collected, whether solicited or spontaneously reported by the subject. After 30 days following the last dose of study drug, only spontaneously reported SAEs will be collected (nonserious AEs will not be collected). In addition, study procedure-related serious and nonserious adverse events will be collected from the time the subject signs the study-specific informed consent.

If a subject prematurely discontinues study participation and begins commercially available upadacitinib (Rinvoq), all AEs reported by healthcare professionals or the patient will be captured as post-marketing reports. The 30-day follow-up phone call following the last dose of upadacitinib study drug during the study will not occur for subjects who begin commercially available upadacitinib.

The following definitions will be used for Serious Adverse Reactions (SAR) and Suspected Unexpected Serious Adverse Reaction (SUSAR):

SAR Defined as all noxious and unintended responses to an IMP related to any dose

administered that result in an SAE as defined above.

SUSAR Refers to individual SAE case reports from clinical trials where a causal

relationship between the SAE and the IMP was suspected by either the sponsor or the investigator, is unexpected (not listed in the applicable Reference Safety

Information), and meets one of the above serious criteria.

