#### **ALL UPA:**

Study drug duration during the administration of study drug in ALL UPA Population is defined as follows.

For All UPA 15mg cohort:

• Date of last dose of upadacitinib 15mg Date of first dose of upadacitinib 15 mg + 1.

For All UPA 30mg cohort:

• Date of last dose of upadacitinib 30mg Date of first dose of upadacitinib 30 mg + 1.

Duration of treatment will be summarized using the number of subjects treated, mean, standard deviation, median, minimum and maximum. In addition, the number and percentage of subjects in each treatment duration intervals ( $\geq 4$  weeks,  $\geq 12$  weeks,  $\geq 16$  weeks, and achieving 24 weeks) will be summarized for Safety 1, Safety 2, and All UPA Populations.

Treatment compliance for DB Period and SB Period will be summarized by treatment groups for Safety 1, and Safety 2 Populations. Treatment compliance is defined as the number of tablets actually taken divided by the number of tablets that should have been taken. For subjects who prematurely discontinued the study drug, the planned tablets will only be counted prior to that scheduled visit of discontinuation. Percent compliance will be summarized.

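### SAP 10.2.4 gives deaths more than 30 days after the last dose as a rate per 100 patient-years of exposure, but that exposure includes no time after the last dose

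*SAP*

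**What the plan says.** SAP 10.2.4 is headed as events per patient-years of exposure and states that "AEs occurring during the entire study will be presented by event rate per 100 patient years", by treatment group. Its list ends with all deaths, split into deaths within 30 days of the last dose, "Deaths occurring > 30 days after last dose of upadacitinib", and deaths related to COVID-19.

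The rate formula is in SAP 10.2.1: 100 times "Number of TEAEs) / (Total Patient Years". In that formula, "total patient years is defined as the sum of the study drug duration", converted to years by dividing by 365.25. SAP Section 6.0 defines duration for each ALL UPA dose cohort as last dose date minus first dose date plus one day. The treatment-emergent window in 10.2.1 runs "through 30 days following the last dose of upadacitinib".

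On data collection, Protocol 6.1 says: "After 30 days following the last dose of study drug, only spontaneously reported SAEs will be collected". The last scheduled contact is the 30-day follow-up visit or call (Protocol 4.1, SAP 2.2). There is one database lock, at the end of the study (SAP 2.2).

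SAP 10.2.2 already gives the same death rows as number and percentage, and 10.2.5 lists deaths.

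**The concern.** In an incidence rate, the events counted must be able to occur in the person-time counted. For deaths more than 30 days after the last dose, none of them can. The numerator lies entirely outside the denominator, so the printed value depends on how much drug was taken and not on how long anyone was observed after day 30. The all-deaths row contains these deaths. The COVID-19 row has no time limit and may contain them.

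This differs from the usual treatment-emergent mismatch, in which events in a 30-day tail are counted but the tail is not. There, most of the time at risk is in the denominator. Here none of it is.

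The stake is a death rate by dose cohort, in a study meant to inform the use of both doses, that could be quoted or compared although it has no rate interpretation.

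**Working it through.** The documents state no death count, death rate or patient-year total, so there is no figure of the plan's own to reproduce. The check applies the SAP formula to the planned study.

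**Inputs**
- 454 subjects, 227 per arm (SAP 2.2 and 2.4; 1:1 randomization).
- Two 12-week periods of 84 days each (SAP 2.2).
- Dropout of at most 8% per 12 weeks (SAP 2.4). *Assumption:* 8% occurs, spread evenly, so average presence is 0.96 in the first period and 0.92 × 0.96 in the second.
- Week 12 split (SAP 2.4): in SS1, 54% move to 30 mg and 46% stay on 15 mg. In SS2, 65% move to 15 mg and 35% stay on 30 mg.

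**Step 1. Person-time in the denominator**
- First period, per arm: 227 × 84 × 0.96 / 365.25 = 50.12 patient-years (PY).
- Second period, per arm: 50.12 × 0.92 = 46.11 PY.
- 15 mg cohort: 50.12 + (0.46 + 0.65) × 46.11 = 101.3 PY.
- 30 mg cohort: 50.12 + (0.54 + 0.35) × 46.11 = 91.2 PY.
- With no dropout, each period gives 227 × 84 / 365.25 = 52.21 PY per arm, so 15 mg has 52.21 × 2.11 = 110.2 PY and 30 mg has 52.21 × 1.89 = 98.7 PY.

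**Step 2. Person-time in which the event can occur**

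Duration ends at the last dose. The time beyond 30 days after the last dose that enters the denominator is 0 PY in both cohorts.

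**Step 3. What one late death would print**

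| Cohort | With 8% dropout | No dropout |
|---|---|---|
| 15 mg | 100 / 101.3 = 0.99 | 100 / 110.2 = 0.91 |
| 30 mg | 100 / 91.2 = 1.10 | 100 / 98.7 = 1.01 |

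These values (per 100 PY) are the same whether subjects were observed for a week or a year after day 30.

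**Step 4. Can a proper denominator be built?**

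No observation time after day 30 is defined. *Assuming* a mean observation time after day 30 for all 454 subjects, one death would give:
- 1 month: 454 / 12 = 37.8 PY, or 2.64 per 100 PY.
- 6 months: 227 PY, or 0.44 per 100 PY.
- 24 months: 908 PY, or 0.11 per 100 PY.

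The documents support no choice within that range. Ascertainment is also uneven. Besides spontaneous reports, Protocol 6.1 has reported adverse events followed to conclusion, and Protocol 5.6 permits public-record survival checks for subjects who withdraw. Subjects who stop early and start commercial upadacitinib get no 30-day call, and their later events become post-marketing reports (Protocol 5.6 and 6.1). None of these routes is systematic or yields person-time.

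**Comparison: the 30-day tail.** It is at most 454 × 30 / 365.25 = 37.3 PY, against 192.4 PY of exposure with dropout (101.3 + 91.2, before rounding) or 208.8 PY without, which is 19% or 18%. That partial mismatch affects the treatment-emergent rows and the row for deaths within 30 days. It is not the point made here.

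**The case against.** The strongest reply is that little turns on this. The study is descriptive with no testing, and few or no deaths are likely. The row label itself shows that the deaths are off drug, and counts, percentages and listings are already planned. All of that stands, and it sets the size of the point. It does not make the printed figure a rate.

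A second reply is that the formula in SAP 10.2.1 is written for treatment-emergent events, which deaths after day 30 are not. That is fair: its use for deaths is inferred from the 10.2.4 heading and from the absence of any other patient-year definition. If another denominator was intended, the SAP does not give it.

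Four stronger readings are tempting but not supported:
- *The rate could grow without limit as reports arrive after the trial.* The table covers the study period, and the single end-of-study lock bounds it.
- *Late deaths are found only by spontaneous report.* Follow-up of reported adverse events and the optional public-record checks are further routes. A footnote naming spontaneous reports alone would be inaccurate.
- *A pooled rate would be printed.* SAP Section 4.0 and Table 1 give ALL UPA results by the 15 mg and 30 mg cohorts, with no pooled group.
- *A known mortality signal makes this serious.* Protocol 2.2 reports that signal for a different JAK inhibitor, in older rheumatoid arthritis patients with cardiovascular risk. It says upadacitinib data have not indicated a higher risk of death versus adalimumab in that disease.

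**Conclusion.** The point holds as a minor reporting defect. Followed as written, SAP 10.2.4 would print a per-100-patient-year figure for deaths more than 30 days after the last dose with zero corresponding person-time, and the all-deaths and COVID-19 rows can carry the same deaths. Conditional on one late death, the figure would be about 1.0 (15 mg) or 1.1 (30 mg) per 100 PY, or about 0.9 and 1.0 with no dropout. This rests on the planned sample size, the planned Week 12 split, evenly spread dropout, and the inference that the 10.2.1 denominator applies to deaths. No direction of bias can be claimed, because the observation time after day 30 is undefined. No efficacy result and no death count is affected.

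**What to change.** In SAP 10.2.4:
- Drop the per-100-patient-year figure for all deaths, deaths more than 30 days after the last dose, and COVID-19-related deaths. Show these as counts and percentages, as in 10.2.2.
- Keep the rate for treatment-emergent events leading to death. Note that this row is defined by onset of the event in the treatment-emergent window, so the death itself may fall later.
- Add a footnote that deaths more than 30 days after the last dose were not systematically ascertained, and came mainly from spontaneous reports and follow-up of ongoing adverse events.

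The cost is a short SAP edit and a change to one table shell. Data collection, endpoints and listings are unchanged, and no information is lost.
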